2.3.2 Known Potential Benefits

The high frequency of visits and the uniform application of prescribed procedures are expected to produce an increased number of wound closures in both groups (the "placebo effect"). The additional anticipated immediate benefit from TTAX01 is a more rapid and higher proportion of healing of the open diabetic foot ulcer. The associated long term benefits are expected to be a reduced risk of recurrent osteomyelitis and of major amputation.

The standard care provided in this protocol is based on guidelines and recommendations from experts in the field of diabetic foot ulcer care. The initial aggressive surgical debridement in an operating room is considered best practice for the type of wounds being studied, which extend to deep subdermal structures and include evidence of associated osteomyelitis. All Investigators are skilled and experienced in the debridement techniques required by the protocol. The test article is made to Good Tissue Practices standards as well as Good Manufacturing Practices.

2.3.3 Assessment of Potential Risks and Benefits

The balance of risks and benefits appears favorable. An opportunity to add other therapies is provided following the first 8 weeks on study if certain criteria are met. Weekly visits for evaluation of both safety and efficacy serve to limit risk.

3 OBJECTIVES AND ENDPOINTS

OBJECTIVES	ENDPOINTS	JUSTIFICATION FOR ENDPOINTS			
Primary					
To determine whether treatment of high grade DFU with standard care plus TTAX01 results in a higher probability of achieving complete wound closure over 26 weeks, compared with standard care alone.	Time from baseline to initial observation of healing, over 26 weeks, where healing has been confirmed at two consecutive visits each two weeks apart.	The endpoint complies with FDA guidance. Dropouts should be minimal during the first 26 weeks, but may increase thereafter. Analysis will use a Cox proportional hazard model			
Secondary					
To compare differences between treatment groups in proportions of wounds healed through 50 weeks	Proportions of wounds healed by Week 50	This endpoint provides insight into longer term benefits of the intervention			
To compare long term durability of closure between treatment groups	Proportions of wounds that re-ulcerate by Week 50	May provide insight into the quality of healing			
To compare limb preservation between treatment groups	Proportions of minor (portions of the foot) and major (ankle, above or below the knee) amputations following the initial procedure by Week 50	Each amputation risks loss of mobility, with consequent increased mortality			
To compare patient reported mobility (lower extremity function) between groups.	Total score on PROMIS Health Organization Neuro- QoL "Lower Extremity Function" at Study End.	The tool is an NIH validated measure of patient reported outcomes			
Safety					
To examine Quality of Life endpoints related to therapeutic intervention	Total score of quality of life assessment determined by Cardiff Wound Impact Schedule (CWIS) at Study End				
Proportion of subjects experiencing adverse events, by group	Spontaneously reported and elicited adverse events, coded in MedDRA				

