Description of Study Intervention:	Subjects randomized to the control and intervention arms will receive aggressive debridement at baseline, followed by 6 weeks of systemic antibiotics plus standard wound care, including off-loading. Subjects randomized to the intervention arm will also receive TTAX01, a cryopreserved human umbilical cord product derived from human placental tissue. Test article is applied and surgically fixed in direct contact with the wound surface, at no shorter than 4 week intervals or when replacement of dislodged material is necessary, unless progress towards healing is evident.
Study Duration: Participant Duration:	The entire study is expected to last for approximately 28 months, from first subject enrolled to last subject completed. Each subject will be in the study for 50 weeks following randomization.

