8.1.9 Confirmation of Closure ("C" Visits)

[Purpose:] These visits serve to confirm that a wound has achieved complete closure

Confirmation of Closure visits are used to record the initial observation of closure, and persistent closure. Ideally, a wound that shows initial closure will still be closed at a confirmation visit two weeks later, and at a second confirmation visit four weeks later. At each of the confirmatory visits, use the Confirmation of Closure visit form(s) to record observations. Continue with the off-loading device appropriate to the location of the ulcer during the period of confirmatory visits.

Perform the following procedures:

- Assess adverse events
- Review concomitant medications
- Assess subject compliance regarding off-loading since the last visit

- Obtain photographs of the ulcer using the electronic wound imaging and measuring device
- Observe the wound if it is fully epithelialized with no drainage or need for a dressing, record it as closed.

If the wound is found to be open at either confirmation visit or if the subject misses a scheduled confirmation visit, record it as such and then move directly to the original schedule of visits. This may become a treatment visit for example if the subject has not passed Visit 16, or an observation visit if the subject has passed Visit 16.

If the index ulcer is closed at the first confirmation visit, schedule the subject to return for a second consecutive confirmation visit in 14 ± 2 days. If the index ulcer remains closed at the second confirmation visit, schedule the subject to begin the Long Term Observation Period at the next study day that will put the subject onto the planned 28 day schedule of visits. For example, if a subject completes the second confirmation visit on Day 50, they should return on Day 64 and continue thereafter with visits every 28 ± 3 days. Days 92, 120, 148, 176, 204, or 232 are the other days on which these subjects can enter into Long Term Observation. Note that Day 176 has a unique window of plus or minus 2 days, otherwise these visits have windows of plus or minus 3 days.

If the initial closure is observed at Visit 28 or 29, the subject should move immediately to the End of Study procedures once both confirmation visits are completed, or if the wound is found to be open at either of the two confirmatory visits.

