9 STATISTICAL CONSIDERATIONS

9.1 Statistical Hypotheses

• Primary Efficacy Endpoint(s):

The primary efficacy endpoint is time in weeks from baseline to the initial observation closure of a complete wound healing, over 26 weeks, that is confirmed at two consecutive visits each two weeks apart. The primary efficacy endpoint will be analyzed using the Cox regression analysis (i.e., proportional hazards model) to assess the effect of TTAX01 treatment on time to complete wound healing compared to SC in terms of hazard ratio and difference in the curve of the proportion of subjects reaching the complete wound healing over the 26-week treatment period.

The null hypothesis is that the hazard ratio of TTAX01 arm vs, SC arm is not statistically different from 1.0. The alternative hypothesis is that the hazard ratio is lower than 1.0 at the significance level of <0.05.

• Secondary Efficacy Endpoint(s):

Secondary efficacy endpoints in this study include proportions of index ulcers healed by Week 50, proportions of wound re-ulcerations by Week 50, proportions of minor and major amputations by Week 50, and total score of PROMIS Lower Extremity Function Questionnaire at end of study.

For index ulcer healing by Week 50, the null hypothesis is that the proportion of subjects with wound healing will not be statistically different between the two treatment arms of this study at Week 50. The alternative hypothesis is that a greater proportion of subjects in the SC plus TTAX01 arm will have index ulcers healed at Week 50, compared to the SC alone arm.

For index ulcer re-ulceration by Week 50, the null hypothesis is that, among those subjects who have had the index ulcer healed before Week 50, the proportion of subjects with wound re-ulcerated will not be statistically different between the two treatment arms of this study at

Week 50. The alternative hypothesis is that a smaller proportion of subjects in the SC plus TTAX01 arm will have index ulcers re-ulcerated at Week 50, compared to the SC alone arm.

For minor and major amputations by Week 50 following initial procedure, the null hypothesis is that the proportion of subjects receiving minor and/or major amputations will not be statistically different between the two treatment arms of this study by Week 50. The alternative hypothesis is that a smaller proportion of subjects in the SC plus TTAX01 arm will have minor and/or major amputations by Week 50, compared to the SC alone arm.

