9.4.3 Analysis of the Secondary Endpoints

Secondary efficacy endpoints in this study include proportions of index ulcer healed by Week 50, proportions of wound re-ulcerations by Week 50, proportions of minor and major amputations by Week 50, and total score of PROMIS Lower Extremity Function Questionnaire at end of study.

The non-parametric Cochran-Mantel-Haenszel (CMH) test with adjustment for baseline wound size cohort will be used to examine treatment effects for the SC plus TTAX01 arm vs. SC alone arm on proportion of subjects with index ulcer achieving and remaining healed at Week 50, proportion of subjects (among those with complete wound healing before Week 50) with wound re-ulceration at Week 50, and proportion of subjects with minor and/or major amputations by Week 50. Subjects' missing values at Week 50 in these endpoints, due to either no assessment or early termination from the study, will be imputed using the last-observation carry forward (LOCF).

An analysis of covariance model (ANCOVA) with treatment and baseline wound size as effect will be used to analyze total score of PROMIS Lower Extremity Function Questionnaire at end of study. Subjects' missing values in this endpoint, due to either no assessment or early termination from the study, will utilize the assessment collected at the early termination visit.

The analyses of the secondary efficacy endpoints will be performed for the ITT population and PP population as well as the LO population.

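### Re-ulceration is compared as a raw proportion to study Week 50, without regard to time at risk after closure, so a difference in closure timing between arms can pass for a difference in durability

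*Protocol*

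**What the plan says.** Protocol Section 3 gives the objective as "To compare long term durability of closure between treatment groups" and the endpoint as "Proportions of wounds that re-ulcerate by Week 50". Section 9.1 sets a directional hypothesis (fewer re-ulcerations on TTAX01) for "among those subjects who have had the index ulcer healed before Week 50, the proportion of subjects with wound re-ulcerated". Section 9.4.3 tests the "proportion of subjects (among those with complete wound healing before Week 50) with wound re-ulceration at Week 50" by Cochran-Mantel-Haenszel, adjusted for wound-size cohort, with last observation carried forward for missing Week 50 values. I read the measure as cumulative to Week 50, as Section 3 words it.

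The observation period is tied to randomization, not to closure. The synopsis (Section 1.1) states: "Each subject will be in the study for 50 weeks following randomization". Under Sections 8.1.7 and 8.2, a re-opening counts against durability only after closure has been confirmed. Section 8.1.9 places the first confirmation visit about two weeks after first closure and then says to "schedule the subject to return for a second consecutive confirmation visit in 14 ± 2 days", so the re-ulceration clock starts about four weeks after first closure. For late closers the same section says: "If the initial closure is observed at Visit 28 or 29, the subject should move immediately to the End of Study procedures". For a wound that stays closed, this step follows the second confirmation. No section sets an equal window after closure, uses person-time, or measures time to re-ulceration from closure.

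**The concern.** A wound first closed at Week 8 is observed for 50 − 8 − 4 = 38 weeks after confirmation. One first closed at Week 30 is observed for 50 − 30 − 4 = 16 weeks. Both count equally in the proportion. Two arms with identical durability will therefore show the same proportion only if their healers close at similar times. The trial's primary endpoint is time to healing, and Section 2.3.2 anticipates faster healing on TTAX01, so similar timing cannot be taken for granted.

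At stake is the reading of a named secondary endpoint. A real durability benefit could be masked, or an apparent benefit or deficit could reflect only when wounds closed. Because Sections 3, 9.1 and 9.4.3 fix the endpoint, denominator, cut-off and test, an analysis plan that follows them inherits the problem.

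**Working it through.** **The plan's own figure.** The protocol gives no figure for re-ulceration. Its only calculation (Section 9.2) supplies the healing rates: 40% on control and 65% on TTAX01. The implied healing hazard ratio is ln(0.35)/ln(0.60) = 2.055. Freedman events at 0.025 in each tail and 90% power are (1.960 + 1.282)² × (3.055/1.055)² ≈ 88.1, rounded up to 89. Then 89/0.525 = 169.5, or 84.8 per arm, and × 1.10 gives 93.2, rounded up to the stated 94. The rates are used below as planned.

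**Common set-up.** Let t be the week of first closure. Time at risk is r(t) = max(0, 50 − t − 4). With the same constant weekly re-ulceration hazard h in both arms, the expected proportion is the mean of 1 − exp(−h·r(t)) over the closure times of healers. The values h = 0.5%, 1% and 2% per week are assumptions. Healing curves come from a cumulative hazard H(t), with the proportion healed equal to 1 − exp(−H(t)).

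**Curves**
- *Exponential:* control −ln(0.60)/26 = 0.01965 per week; TTAX01 −ln(0.35)/26 = 0.04038 per week. Closures are counted to Week 50, then again only to Week 46, the last week that allows confirmation by Week 50.
- *Early then plateau, proportional hazards:* shape from the real-world data in Section 2.2 (34.7% healed by 16 weeks, 42.5% by one year). H is piecewise linear through −ln(0.653) = 0.426 at Week 16 and −ln(0.575) = 0.553 at Week 52, which gives 0.461 at Week 26. It is scaled by 0.511/0.461 = 1.107 so that control reaches 40% at Week 26. TTAX01 is 2.055 times that.
- *Cross-study illustration:* control is the real-world curve unscaled. TTAX01 passes through 50% at Week 16 (the Phase 2 study) and 78.8% (the retrospective osteomyelitis series, placed at Week 52 by assumption). By Week 16, 34.7/42.5 = 82% of control healers have closed, against 50/78.8 = 63% of cord-treated healers.

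**Results with identical durability (control vs TTAX01)**

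| Healing curve | Mean weeks at risk | h = 0.5% | h = 1% | h = 2% | TTAX01 minus control, points |
|---|---|---|---|---|---|
| Exponential, to Week 50 | 25.1 vs 28.9 | 11.6% vs 13.3% | 21.5% vs 24.5% | 37.1% vs 41.9% | +1.7, +3.0, +4.8 |
| Exponential, to Week 46 | 26.4 vs 29.7 | 12.2% vs 13.7% | 22.6% vs 25.2% | 39.0% vs 43.1% | +1.5, +2.6, +4.1 |
| Early then plateau | 34.3 vs 36.0 | 15.6% vs 16.4% | 28.6% vs 29.9% | 48.3% vs 50.2% | +0.8, +1.3, +1.9 |
| Cross-study | 34.2 vs 30.5 | 15.6% vs 14.0% | 28.5% vs 25.7% | 48.1% vs 43.7% | −1.6, −2.8, −4.4 |

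If TTAX01 raised only the share healed and left timing among healers unchanged, the gap would be zero.

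**Effect on the test.** Take the exponential curve, closures to Week 46, 125 per arm and an assumed 40% annual re-ulceration (−ln(0.60)/52 = 0.98% per week). In simulation, an unstratified two-proportion test was falsely significant against TTAX01 in 5.9% of trials and in its favour in 1.0%; nominal is 2.5% each.

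**Check of the remedy.** Counting re-ulceration over an equal 12 weeks from confirmed closure gives 1 − exp(−0.0098 × 12) = 11.1% in both arms, and the simulated error rates are 2.3% and 2.8%.

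**The case against.** A reader might infer that the endpoint is biased against TTAX01 whenever the primary hypothesis is true, and derive from the exponential curve a single hazard reduction that TTAX01 would need just to tie. The documents do not support that. Among healed wounds the bias depends on closure timing among healers, not on the share healed. Section 9.2 gives two healed proportions and no curve. Exponential healing implies 1 − exp(−0.01965 × 50) = 62.6% of controls healed by Week 50, against 42.5% at one year in the real-world data of Section 2.2. With that section's own patterns the sign reverses, although that comparison crosses studies and is only illustrative.

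It might also be inferred that wounds first closed in about Weeks 46 to 50 certainly enter the denominator with no time at risk. They do have little or none. But their second confirmation falls at about Weeks 50 to 54, and the text does not settle whether they count as healed before Week 50.

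The effect is also modest. With about 125 × 0.626 = 78 and 125 × 0.867 = 108 healers, the standard error of the difference at h = 1% is √(0.215 × 0.785/78 + 0.245 × 0.755/108) ≈ 6 points, about twice the 3.0-point gap. Section 3 claims only that the endpoint may give insight into the quality of healing. Cumulative re-ulceration by a fixed study week is a legitimate description, and Section 9.4.1 leaves detailed methods and sensitivity analyses to the analysis plan.

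These arguments limit size and direction. They do not supply an adjustment for time at risk, and a bias whose sign depends on closure timing is itself a reason not to read the comparison as durability.

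**Conclusion.** The point holds in a limited form. As written, the comparison mixes durability with time at risk whenever closure timing among healers differs between arms. With identical durability, the distortion runs from about 5 points against TTAX01 to about 4.5 points in its favour. This range rests on assumed re-ulceration hazards of 0.5% to 2% per week, constant and common to both arms, and on healing curves that the protocol does not specify. No single direction or tie figure should be quoted. The primary analysis is untouched. This is an inexpensive improvement to a secondary endpoint, not a threat to the trial's main conclusion.

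**What to change.** In Sections 1.1, 3, 9.1 and 9.4.3, define durability as time from confirmed closure (the second confirmation visit) to first re-ulceration, censored at the last wound assessment. Compare arms by log-rank test or Cox model stratified by wound-size cohort. If a percentage is preferred, use the Kaplan-Meier proportion re-ulcerated within a fixed window after confirmed closure, such as 12 or 24 weeks. State whether wounds first closed in about Weeks 46 to 50 belong to the analysis. The Week 50 proportion can remain as a descriptive figure.

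The cost is wording and programming, since closure and re-opening are already recorded at dated visits. The result is less simple than one Week 50 percentage. The change also leaves a separate problem in place: healed subjects are selected after randomization, and comparing them is not a randomized comparison whichever clock is used.

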4 STUDY DESIGN

4.1 Overall Design

The hypothesis under study is that one or more applications over 16 weeks of TTAX01, to the wound surface of a well debrided, complex diabetic foot ulcer managed with appropriate antibiotic therapy will result in a higher probability of complete healing than would be expected from management with standard care alone. In this controlled Phase 3 trial, all subjects will receive standard care throughout the entire study, with the option to add one or more additional therapies if healing is inadequate ($\leq 50\%$ reduction in area) after 8 weeks.

Eligible consenting subjects will undergo a baseline aggressive debridement in the operating room to remove infected and devitalized bone and soft tissue. A six week course of systemic antibiotics will be used to resolve baseline infection following recommendations from the Infections Diseases Society of America (IDSA) guidelines. For subjects randomized to the treatment group, TTAX01 will be applied during the surgical procedure to the debrided wound bed at baseline, and if healing is not evident, it will be applied again at intervals no shorter than 4 week or when replacement of dislodged material is necessary. At each visit the wound will be further debrided as necessary for subjects in both groups.

Surgical debridement at the baseline visit will include biopsies of bone for histology and microbiologic testing, at the start and completion of debridement. This debridement may involve resection of necrotic bone and performance of minor amputations. Systemic antibiotics may be given empirically from the first Screening visit, with adjustments made on the basis of culture and sensitivity results. New or recurrent infections will be managed with additional debridement and adjustment or addition of appropriate systemic antibiotics. For subjects randomized to the treatment group, the test article, TTAX01, will be fixed with sutures, staples or both to the debrided wound bed at baseline and again at no less than 4 week intervals over the 16 week treatment period for wounds that do not show evidence of healing. For wounds in this group that do show evidence of healing, additional applications of TTAX01 will be withheld, week by week.

Subjects whose wounds close at any time during the trial will move to a series of two consecutive confirmation of closure visits, two weeks apart, then continuing with monthly observational visits until the end of the study, unless the first observation of closure is at the final visit, in which case their participation in the study will extend out to 54 weeks, moving to a series of two consecutive confirmation of closure visits, two weeks apart.

4.2 Scientific Rationale for Study Design

The standard two-group parallel design is consistent with the CONSORT statement, being generally agreed to generate valid outcomes data when conducted with appropriate rigor. The inability to blind the treatment is a shortcoming, overcome in large part by the objective nature of the endpoint measurement, the use of multiple investigative sites, and the additional use of blinded, third party reviewers.

4.3 Justification for Dose

Dosing quantity is determined by the natural thickness of the product, while dosing frequency is informed by the clinical trials summarized in the Background section.

The form of the test article is suitable for application directly to the surface of the wound, surgically fixed with sutures or staples. Ideally, the test article will cover the entire wound surface. Dosage is understood to be a function of the thickness of the test article, from which intermediary molecules such as HC-HA/PTX3 should diffuse into the adjacent tissue.

4.4 End of Study Definition

A subject is considered to have completed the study if he or she has completed the final long term observation visit (Visit 29), shown in the Schedule of Activities (SoA), Section 1.3.

5 STUDY POPULATION

Adult subjects aged ≥18 year-old with reasonably controlled diabetes mellitus and a complex non-healing DFU with high risk factors of [1] ulcer depth indicating exposed bone, tendon, muscle, and/or joint capsule and [2] clinical suspicion of osteomyelitis will be recruited for this trial. The majority of subjects (220) will come from US sites, with an additional 30 expected to be enrolled at three sites in Taiwan.

5.1 Inclusion Criteria

In order to be eligible to participate in this study, an individual must meet all of the following criteria in a maximum of two screening attempts:

- 1. The subject has signed the informed consent form
- 2. The subject is male or female, at least 18 years of age inclusive at the date of Screening
- 3. The subject has confirmed diagnosis of Type I or Type II diabetes
- 4. The subject's index ulcer is located on the plantar surface, inter digital, heel, lateral or medial surface of the foot
- The subject has an index ulcer with visible margins having an area ≤ 12.0 cm² when measured by the electronic measuring device at Screening
- 6. The subject's index ulcer extends beyond the dermis, into subcutaneous tissue with evidence of exposed bone, tendon, muscle and/or joint capsule
- 7. The subject presents with history, signs or symptoms leading to a clinical suspicion of osteomyelitis in the opinion of the Investigator supported by positive Probe to Bone (PTB) and any of the following: radiographic (X-ray, Magnetic Resonance Imaging (MRI), or bone scan) or evidence of bone necrosis
- 8. The subject has an ABI \geq 0.7 to \leq 1.3 or TcPO2 \geq 40 mmHg on the dorsum of the affected foot, or Great Toe Pressure \geq 50 mmHg
- 9. The subject is under the care of a physician for the management of Diabetes Mellitus
- 10. The subject is willing to return for all mandatory visits as defined in the protocol

11. The subject is willing to follow the instructions of the trial Investigator

